Study Visit 5 will occur 9 months ( $\pm$  15 days) after initiation of the intervention (study drug initiation). The following procedures will be performed during this visit:

- Symptom/adverse events assessment
- Medical history
- Concomitant medications review
- Health assessment
- Imaging review
- Study Agent
  - Collect study agent and diary
  - Assess compliance (pill count)
  - Review study diary
  - o Dispense study agent (one new bottle of 120 capsules) and diary

## 6.2.7 Study Visit 6

Study Visit 6 will occur 12 months ( $\pm$  15 days) after initiation of the intervention (study drug initiation). The following procedures will be performed during this visit:

- Symptom/adverse events assessment
- Medical history
- Concomitant medication review
- Physical assessment
- Clinical blood specimen
  - Blood Chemistry
    - o Lipid
    - o Hba1c
    - o PT/INR
    - o AFP
- Research blood specimen
- Imaging review
- Liver stiffness
- Liver fat fraction
- Follow-up risk factor questionnaire
- Study agent
  - Collect study agent and diary
  - Assess compliance (pill count)
  - Review study diary

**6.2.8** Unscheduled Visit (Transplant Specimen Collection). For all patients who enter the trial and receive a liver transplant before the end of this study, we will obtain specimens at the time of transplantation. The research blood specimen will be collected prior to transplant (while the patient is being prepped for surgery).

- Research blood specimen
- Transplant tissue specimen

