## 6.7 Removal of Subjects from Study

Patients can be taken off the study treatment and/or study at any time at their own request, or they may be withdrawn at the discretion of the investigator for safety, behavioral or administrative reasons. The reason(s) for discontinuation will be documented and may include:

- Patient voluntarily withdraws (follow-up permitted);
- Patient withdraws consent (termination of treatment and follow-up);
- Patient is unable to comply with protocol requirements;
- Patient demonstrates recurrence of HCC (unless continued treatment with study drug is deemed appropriate at the discretion of the investigator);
- Patient experiences toxicity that makes continuation in the protocol unsafe;

- Treating physician judges continuation on the study would not be in the patient's best interest;
- Patient becomes pregnant (pregnancy to be reported along same timelines as a serious adverse event);
- Development of second primary malignancy (basal/squamous cell skin cancer, or prostate cancer with a Gleason score 6 or less) that requires treatment, which would interfere with this study;
- Lost to follow-up. If a research subject cannot be located to document survival after a period of 2 years, the subject may be considered "lost to follow-up." All attempts to contact the subject during the two years must be documented and approved by the Data Monitoring Committee.

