## 9.1 Randomization/Stratification

Patients will be randomized by the Research Pharmacy at each site. Randomization will be carried out among consented patients meeting the Screening Visit eligibility criteria at each site with a 1:1 ratio for pravastatin and placebo assignment, by blocks based on clinical site and initial HCC treatment type.

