## 9.3.1 Analysis of Primary Endpoint: TTR

The log-rank test will be carried out to compare the distributions of TTR between placebo and pravastatin groups and the Kaplan-Meier estimators will be presented graphically. Cox proportional hazards model will be fitted to the data where the explanatory variable of interest is the indicator of treatment allocation adjusting for clinical and demographic baseline covariates, including sex. Patients who did not experience HCC recurrence, or receive a liver transplant and are still alive at the end of the study will be right censored. Patients who are transplanted or die before HCC recurrence will be treated as a competing risk. A competing risk model for TTR will be used to estimate the cumulative incidence of TTR using time to transplant or death as a competing risk. The proportional hazards assumption will be tested graphically and analytically, and model diagnostics such as martingale and Schoenfeld residuals will be conducted to assess model adequacy. Violation of the proportional hazards assumption will be addressed by use of time-dependent covariates or extended Cox models. The possibility of collinearity among the explanatory variables will be reduced after careful assessment of the correlation matrix and condition index. Automatic variable selection methods in a multivariable Cox proportional hazards model such as stepwise, backward, and forward will be used as a guideline to identify sets of important predictors and a more rigorous approach based on a 4-step procedure outlined in Collett (2003) will be employed (55). Power. Preliminary data indicate that the 12-month RFS is between 57% and 78% in patients with: 1) Child Pugh A or B cirrhosis, 2) small HCCs (typically meeting Milan criteria) 3) liver directed therapy (typically RFA or resection), and 4) no other interventions (27, 56-59). Therefore, we will assume that the 12-month RFS in the control group is 65%. Assuming a common cumulative incidence of the competing risk events at 12 months of 20% (10% due to liver transplant and 10% due to death), a 42-month accrual time and 15-month follow up time, and 10% drop out, data from 47 patients per group achieve 80% power to detect a hazard ratio of 0.45 using a two-sided log-rank test with a 0.1 level of significance. This is equivalent to detecting a decrease in the 12-month cumulative incidence of disease recurrence from 35% in the control group to 18% in the treatment group, which is clinically meaningful. The choice of a type I error rate of 0.1 is appropriate for a randomized phase II trial since this can serve as a randomized screening design for a nondefinitive comparison of statin vs placebo (reference: Mandrekar and Sargent (2010)). We further assumed that TTR and time to death or transplant are independent and exponentially distributed. Statistical power was based on the formulas in Machin et al. (2008) and Pintilie (2006) and were carried out using PASS version 13 (60, 61).

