**Change in biomarkers.** Two-sample t-test will be carried out to compare the change in biomarkers from baseline to each of the two follow-up time points, 6 and 12 months, between treatment and placebo groups. The Man-Whitney test will be used in the presence of highly skewed distributions and Fisher exact test will be used for dichotomous stratifications (high versus low). Assuming a common standard deviation of the change in biomarker from baseline to each time point between the two groups SD(diff), data from 47 patients per group achieve 80% power to detect an effect size of 0.72 using a two-sided two-sample t-test with a Bonferroni corrected 0.01 level of significance since we plan to test 10 biomarkers (0.1 / 10). Here, the effect size is the ratio between the difference in change of biomarkers between the two groups over SD(diff). Linear or logistic regression analysis will be carried out if there is evidence of imbalance between the two groups with respect to one or more baseline clinical and demographic covariates at each time point as in Aim 3.

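### The month-12 biomarker test uses only patients with a Visit 6 blood sample and makes no use of month-6 values; if patients leave at recurrence, power is about 56% rather than 80%, and the unequal loss can bias the comparison.

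*Combined protocol and SAP*

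**What the plan says.** Secondary objective 6 (section 2.2) asks for the effect of pravastatin on change in serum biomarkers at 12 months. Section 2.3 lists ten markers. The schedule in section 6.4 places research blood at months 0, 6 and 12.

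Section 9.3.2 will "compare the change in biomarkers from baseline to each of the two follow-up time points, 6 and 12 months", by t-test or, for skewed data, a rank test. The power statement is "data from 47 patients per group achieve 80% power to detect an effect size of 0.72". The test level behind it is 0.01, two-sided: an overall 0.1 divided among ten markers by Bonferroni. Regression for baseline imbalance is the only other model, and it too is run one time point at a time. Section 9 gives no missing-data method, no repeated-measures model and no analysis population for biomarkers.

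On who is still sampled at month 12, the sections differ:

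- Section 6.7 lists as a removal reason: "Patient demonstrates recurrence of HCC (unless continued treatment with study drug is deemed appropriate at the discretion of the investigator"). Its opening is permissive.
- Section 5.10 is firmer. Patients meeting a 6.7 criterion leave the study and are followed under section 6.3, which consists of telephone calls.
- Section 6.6 says patients off agent are followed for endpoint data where possible. The data it goes on to name are chart data, not research blood, and its list of off-agent reasons does not include recurrence.
- Section 2.3 makes transplanted patients ineligible. Section 6.2.8 adds a blood sample at that point ("The research blood specimen will be collected prior to transplant (while the patient is being prepped for surgery"), for which section 9 states no use.

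**The concern.** A month-12 change score needs a month-12 sample. If patients who recur do not give one, the test compares those who stayed recurrence-free, untransplanted and alive, not the randomised arms. The plan itself expects recurrence to differ by arm: section 9.3.1 is powered for a "decrease in the 12-month cumulative incidence of disease recurrence from 35% in the control group to 18% in the treatment group". The missing group would then be related to outcome and unequal in size.

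Two things are at stake. The first is power, because the 47 per arm is carried over from the time-to-recurrence calculation. There a recurrence is an event; for a month-12 measurement it is a lost patient unless blood is still drawn. The second is bias, because a t-test on those remaining is safe only if leaving is unrelated to the marker. Most patients who leave between months 6 and 12 will have a month-6 sample, which the month-12 test cannot use.

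**Working it through.** **Inputs.** Allocation is "with a 1:1 ratio for pravastatin and placebo assignment", 65 per arm (9.1, 9.2). Effect is 0.72 in units of SD(diff), with a common SD (9.3.2: "Assuming a common standard deviation of the change in biomarker from baseline to each time point between the two groups SD(diff")). Alpha is 0.1/10 = 0.01, two-sided. By 12 months, recurrence is 35% on placebo and 18% on pravastatin, transplant plus death is 20% in both arms, and drop-out is 10% (all 9.3.1).

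**1. The plan's figure.** Noncentrality = 0.72 / √(1/47 + 1/47) = 3.49 on 92 degrees of freedom, with critical t 2.63. Exact noncentral-t power is 80.3%, so the stated 80% reproduces.

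**2. Where 47 comes from.** 65 × 0.80 × 0.90 = 46.8. Competing events and drop-out are subtracted; recurrences are not. Sections 3.0 and 9.2 agree: section 3.0 names transplantation and cirrhosis death, and 130 × (1 − 0.28) = 93.6.

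**3. Month-12 numbers if recurrences leave.**

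| Reading | Placebo | Pravastatin | Power at 0.72 | Effect for 80% power |
|---|---|---|---|---|
| Recurrences still sampled | 46.8 | 46.8 | 80% | about 0.72 |
| Leave; 35%/18% as cumulative incidence | 65 × (1 − 0.35 − 0.20) × 0.9 = 26.3 | 65 × (1 − 0.18 − 0.20) × 0.9 = 36.3 | 56% | 0.90 |
| Leave; 35%/18% as net risks | 65 × 0.65 × 0.80 × 0.9 = 30.4 | 65 × 0.82 × 0.80 × 0.9 = 38.4 | 62% | 0.855 |

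In the second row, noncentrality is 0.72 / √(1/26.3 + 1/36.3) = 2.81 against critical t 2.66. Retention is 26.3/65 = 40% and 36.3/65 = 56%. This row is the low end: it supposes that no recurrent patient gives Visit 6 blood, not even one whose recurrence is first seen on the month-12 scan.

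**4. Unused month-6 values.** With a constant rate of loss, 65 × √0.405 = 41.4 placebo and 65 × √0.558 = 48.6 pravastatin patients remain at month 6. About 41.4 − 26.3 = 15 and 48.6 − 36.3 = 12 patients would then have a month-6 value that plays no part in the month-12 test.

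**5. Bias, and what a repeated-measures model recovers.** Simulation, 4,000 runs per scenario, using the second row's numbers. The following are assumptions, not document figures: true effect −0.72 SD, fully present by month 6; correlation of the month-6 and month-12 changes 0.3, 0.5 or 0.7; random loss before month 6; selection of 1 log-odds per SD after it. Ranges run across the three correlations.

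| Loss after month 6 depends on | t-test estimate | Model estimate | t-test power | Model power |
|---|---|---|---|---|
| Nothing (random) | −0.71 to −0.73 | −0.71 to −0.73 | 57%, 54%, 56% | 57%, 58%, 64% |
| Worse month-6 value, both arms | −0.66 to −0.70 | −0.72 | 52%, 52%, 50% | 56%, 60%, 64% |
| Worse unseen month-12 value, both arms | about −0.63 | −0.64 to −0.67 | 51%, 50%, 50% | 52%, 55%, 63% |
| Worse month-6 value, pravastatin only | −0.79 to −0.87 | −0.72 | 65%, 71%, 77% | 56%, 58%, 64% |
| Better month-6 value, both arms | −0.76 to −0.79 | −0.72 to −0.73 | 62%, 64%, 69% | 58%, 59%, 64% |

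In the first three rows the model gains about 0 to 14 points. In the last two the t-test looks more powerful only because its estimate is exaggerated.

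**The case against.** The strongest reply is that the plan may intend recurrent patients to keep giving blood. Section 6.6 promises endpoint data on the schedule of events, which includes month-12 research blood. Section 6.7 is permissive and has an investigator exception. The 47 per arm is exactly what follows if no recurrence is lost. On that reading power is 80% and the expected imbalance disappears. This stands as a possible reading, so the shortfall is conditional. It does not settle the matter, because section 5.10 sends patients removed under 6.7 to telephone contact, and section 6.6 neither lists recurrence nor names research blood.

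A reader might infer several stronger things that the documents do not support:

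- **That transplants and deaths also differ by arm.** Section 9.3.1 assumes a common 20%; only recurrence is expected to differ.
- **That the effect is certainly biased towards zero.** This needs worse markers to go with recurrence, which is plausible but not shown. Other loss patterns give no bias or the reverse. The hypothesis in section 1.3 also lets markers move either way, so the worse direction is not defined for each marker.
- **That month-6 samples are wasted.** They have their own between-arm test; they are only missing from the month-12 comparison.

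It is also fair to say that most of the power loss comes from lost patients, which no model replaces, and that this is one secondary objective of a Phase II screening trial.

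**Conclusion.** The point holds in conditional form. By construction the month-12 test is limited to patients with a Visit 6 sample, has no missing-data method and takes nothing from month 6. If recurrences leave, about 26 placebo and 36 pravastatin patients remain and power is about 56% (62% with net risks). If all recurrent patients still give month-12 blood, it is 80%. The truth lies between, depending on a sampling rule that the plan does not settle. These power figures rest on the plan's own rates and on removal at recurrence, not on any link between marker and outcome.

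Bias is possible, most plausibly towards zero if worse markers go with recurrence. In the simulated cases of that kind the t-test gave −0.63 to −0.70 against a true −0.72. Those sizes rest on assumed correlations and selection strength and are illustrations, not estimates for this trial.

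The change should be made: the alternative uses samples already scheduled and needs a weaker missing-data assumption than the t-test on patients who remain.

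**What to change.** In section 9.3.2, before unblinding:

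1. Replace the per-visit t-tests with one likelihood-based repeated-measures model per marker. Use months 0, 6 and 12, treatment-by-visit terms and an unstructured covariance, on a log scale if skewed. Include all randomised patients with a baseline value, and take the month-12 contrast as the result.
2. State whether research blood is drawn after recurrence, and reconcile sections 5.10, 6.3, 6.6 and 6.7 on that. This concerns sampling only, not whether study drug continues.
3. State how recurrence, transplant and death before month 12 are handled. The model does not by itself define a marker value after death or transplant.
4. Add a not-at-random sensitivity analysis, for example delta-adjusted. Ranking recurrences and deaths as worst is not suitable, since it would turn a biomarker test into a test of recurrence.
5. Restate power at the expected month-12 numbers.

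The cost is mainly SAP wording and some extra analysis. The model itself needs no new visits or samples. Its limits are that it assumes data missing at random, corrects only in part when loss depends on the unseen month-12 value, recovers about 0 to 14 power points and does not restore 80%.

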#### 5.3 Blinding/Unblinding

Due to the objectives of the study, the identity of test and control treatments will not be known to investigators, research staff, or subjects. The following study procedures will be in place to ensure double-blind administration of study treatments.

- The study biostatisticians will set up randomization blocks.
- After registration, participants will be randomized to treatment with the study agent or placebo
- Investigators and participants will be blinded as to the result of randomization. The following people will be unblinded: the study biostatisticians at Cedars-Sinai and the investigational pharmacists at each participating site.
- The investigational pharmacist will manage the study agent and placebo.
- Unblinding will only occur when it is deemed medically necessary.

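### The biomarker comparison fixes no log scale, no baseline adjustment and no skewness criterion; if effects are proportional, a log-scale ANCOVA would use the same data better

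*Combined protocol and SAP*

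**What the plan says.** Section 2.3 (secondary endpoint 6) lists 10 circulating cytokines, chemokines, soluble receptors and proteins. The hypothesis in section 1.3 allows each marker to rise or fall.

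Section 9.3.2, under Change in biomarkers, gives the analysis: "Two-sample t-test will be carried out to compare the change in biomarkers from baseline to each of the two follow-up time points", namely 6 and 12 months. For skew it adds: "The Man-Whitney test will be used in the presence of highly skewed distributions". Fisher's exact test covers high/low splits. Regression enters only if baseline clinical or demographic covariates look unbalanced.

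On power, "data from 47 patients per group achieve 80% power to detect an effect size of 0.72", by a two-sided t-test at 0.01 (0.1 divided by 10 markers). The effect size is the between-arm difference in change divided by a common SD of the change.

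No section mentions a logarithm or other transformation, a ratio to baseline, or routine adjustment for the baseline marker value. The biomarker paragraph does not say how much skew triggers the switch, or whether skew is judged on the levels or on the change. The liver stiffness paragraph of 9.3.2 is more specific: it refers to the distribution of the change and to approximate normality of the sample mean.

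Section 5.3 states: "The following people will be unblinded: the study biostatisticians at Cedars-Sinai and the investigational pharmacists at each participating site".

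**The concern.** Serum concentrations are positive and can be right-skewed, a possibility the plan provides for. If a drug changes such a marker by a proportion, a patient with a tenfold higher baseline shows a tenfold larger arithmetic change for the same drug effect. Patients with high baselines then dominate the variance of the change. A rank test on that same change limits the influence of extreme values but does not put patients on a common scale.

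The trigger is also poorly aimed if it looks at the change score. With no drug effect, the difference of two equally distributed measurements is symmetric however skewed the levels are. It is heavy-tailed rather than skewed, so a skewness check can miss the cases in which the t-test is weak.

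At stake is a named mechanistic secondary objective tested at 0.01 per marker. Power may be lost without need, and results across markers could mix mean differences with rank tests chosen after the data are seen.

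**Working it through.** **Inputs from the documents.** 47 per group; two-sided alpha 0.01; effect size 0.72; 1:1 allocation (sections 9.1 and 9.3.2).

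**Assumed, not in the documents.** Log-normal levels with log-SD s; log correlation ρ between baseline and follow-up; an effect that multiplies the level by a ratio g. CV = √(exp(s²) − 1), so s = 0.2, 0.3, 0.5, 0.8, 1.0 gives CV 20%, 31%, 53%, 95%, 131%.

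**Step 1: the plan's figure.** Noncentral t, d = 0.72, n = 47 per arm, alpha 0.01: power 80.3%. The smallest d for 80% power is 0.718. The stated figure reproduces.

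**Step 2: skewed data, effect as the plan defines it.** With log-normal levels (s 0.25 to 1.0, ρ 0.3 to 0.7) and an additive shift of 0.72 SD of the raw change, the t-test has 80-83% power and Mann-Whitney 81-99.9%. With a proportional effect scaled to a raw effect size of 0.72, they have 80-93% and 79-99.9%. On its own definition the plan keeps its power.

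**Step 3: effect of 0.72 SD of the log change.** The SD of the log change is s√(2(1 − ρ)), so g = exp(±0.72·s·√(2(1 − ρ))). In units of the mean level, the raw change has

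- mean 0 (control) and g − 1 (treated);
- variance v₀ = 2(exp(s²) − exp(ρs²)) (control);
- variance v₁ = (g² + 1)(exp(s²) − 1) − 2g(exp(ρs²) − 1) (treated).

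The raw effect size is (g − 1)/√((v₀ + v₁)/2). At s = 1.0 and ρ = 0.6:

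- Decrease: g = 0.525, v₀ = 1.79, v₁ = 1.33, giving −0.475/1.249 = −0.38.
- Increase: g = 1.904, v₁ = 4.82, giving 0.904/1.818 = 0.50.

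So 0.72 on the log scale shrinks to 0.38 or 0.50 on the raw scale. The SDs of raw change also differ between arms (treated/control √(1.33/1.79) = 0.86 and √(4.82/1.79) = 1.64), against the plan's common-SD assumption.

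**Step 4: simulated power** (ρ = 0.6, 47 per arm, alpha 0.01, 10,000 trials per setting):

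| Direction | CV | t-test, raw change | Mann-Whitney, raw change | t-test, log change | ANCOVA on logs |
|---|---|---|---|---|---|
| Decrease | 20% | 75% | 73% | 80% | 89% |
| Decrease | 31% | 71% | 70% | 80% | 89% |
| Decrease | 53% | 59% | 65% | 81% | 89% |
| Decrease | 95% | 41% | 57% | 81% | 89% |
| Decrease | 131% | 28% | 54% | 80% | 89% |
| Increase | 20% | 81% | 79% | 80% | 89% |
| Increase | 31% | 81% | 80% | 80% | 89% |
| Increase | 53% | 76% | 79% | 80% | 89% |
| Increase | 95% | 63% | 77% | 80% | 89% |
| Increase | 131% | 52% | 77% | 80% | 89% |

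Repeat runs agree within one or two points (for example 53% and 75% for Mann-Whitney at CV 131%).

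**Step 5: why ANCOVA gains.** The residual SD after adjustment for log baseline is s√(1 − ρ²), so the effective size is 0.72·√(2(1 − ρ)/(1 − ρ²)) = 0.72·√(2/(1 + ρ)). At ρ = 0.6 this is 0.805, for which the t-test formula gives 89.5%. Over ρ 0.3 to 0.7, simulated ANCOVA power is 86-96%.

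**Step 6: the procedure with its switch.** The plan gives no threshold, so I assumed Mann-Whitney when absolute skewness of the change exceeds 1. For decreases, power is 73-74% at CV 25%, 60-63% at 53%, 52-55% at 87% and 46-48% at 131%. At CV 53% the switch fires in only 17-20% of those trials.

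**The case against.** A reader might infer that skewed markers cannot reach the stated 80% power, or that the figure holds only for normally distributed change. The documents do not support either reading. The plan defines 0.72 in SDs of the change itself, and step 2 shows that 80% is roughly kept under skew on that definition. The shortfall in step 4 appears only when the effect is proportional and 0.72 is read on the log scale.

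Direction matters too. For proportional increases, which section 1.3 also expects, Mann-Whitney loses little. And the t-test figure of 28% belongs to extreme skew, where the plan may well switch to the rank test.

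The text should not be pressed further than it goes. Skew is named as a contingency, not as an expectation. The word distributions could mean the levels, where skew would be visible. That the change is untransformed is inferred from silence, and section 8.0 refers specimen testing to a Laboratory Manual not available here. Section 5.3 says that the biostatisticians are unblinded, but nothing says that they would judge skewness by arm or after merging the allocation.

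All of this stands, and it limits the point to efficiency and prespecification. It does not answer the gap: scale, criterion and baseline adjustment remain unspecified, and no power is given for the test that would be used under skew.

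**Conclusion.** The point holds as a cheap improvement to one secondary endpoint. It is not an error in the stated power and does not touch the primary endpoint.

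Under the step 4 assumptions, the loss against a log-change t-test runs from almost none to about 50 points for the raw t-test and from about 0 to 30 points for Mann-Whitney. It is largest for decreases in very variable markers. ANCOVA on logs adds about 8 to 10 points over log change at a correlation of 0.6. Log-normality, proportional effect, CV and correlation are all assumed, so the sponsor should check them against its own assay data.

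**What to change.** In section 9.3.2, under Change in biomarkers:

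- State that concentrations are log-transformed and the arms compared at 6 and 12 months by ANCOVA on the log value, adjusted for the log baseline value. Report a ratio of geometric means with confidence interval.
- Delete the skew-triggered switch to Mann-Whitney.
- State that 0.72 refers to the SD of the log change.
- Fix a rule for values below the assay limit before allocation is merged with the data. For a marker with many undetectable values, a rank test on the log ratio could be named instead, also before that merge.

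The cost is wording only: no extra patients, samples or visits. The small downsides are that effects are reported as ratios and that a convention for undetectable values is needed.

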#### • Secondary Efficacy Endpoints

Secondary endpoints include recurrence-free survival (RFS), overall survival (OS), waitlist survival, liver stiffness, liver fat fraction, circulating biomarkers, and liver tissue biomarkers. Differences in secondary endpoints will be compared in the pravastatin and placebo groups.

1) RFS: We will assess the effect of pravastatin on RFS. RFS will be defined as the time from randomization to the first occurrence of a documented HCC recurrence, within the 12-month intervention and assessment period.

2) OS: We will examine the effect of pravastatin on OS (defined as the time from randomization to death from any cause).

3) Waitlist drop-off: We will evaluate the effect of pravastatin on reducing waitlist dropout due to any of the following causes: 1) HCC progression outside of Milan/T2 criteria, 2) cirrhosis progression (too sick to transplant), or 3) death.

Participants who are delisted for other reasons (such as positive alcohol test) will be censored at date of delisting.

4) Change in liver stiffness: We will evaluate the effect of pravastatin on withinperson change in liver stiffness, as measured by magnetic resonance elastography (MRE) or FibroScan, between Study Visit 1 (0 month) and Visit 6 (12 month). Within-patient consistency is required between Study Visits 1 and 6 with regards to liver stiffness testing modality (MRE or FibroScan).

5) Change in liver fat fraction: We will evaluate the effect of pravastatin on withinperson change in liver fat fraction, as measured by MRI-proton density fat fraction (PDFF), between Study Visit 1 (0 month) and Visit 6 (12 month).

6) Change in serum biomarkers of monocyte/macrophage and stellate cell activation: We will examine the effect of pravastatin on change in serum biomarkers including cytokines, chemokines, soluble receptors, and proteins (specifically, IL6, TNF $\alpha$ , sTNFRII, IL18BP, sCD163, IL10, IL17, IL-8, CCL17, TGF $\beta$ ).

7) Levels of liver tissue markers related to HCC: We will examine the effect of pravastatin on levels of liver tissue markers related to HCC including those in the Wnt/ $\beta$ -catenin pathway (specifically,  $\beta$ -catenin and glutamine synthetase).

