## 9.2 Sample Size and Randomization

Sample size: Intervention = 130 (65 statin: 65 placebo) randomized sample; Analytic sample = 94 (47:47) after 28% drop-out. The expected accrual rate is 5 participants per month across three sites (1.6 participants per site), and the planned recruitment duration

is 3 years. We anticipate that all evaluable participants will have completed all study procedures within 4 years. Power and precision arguments are provided below.

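### The serum-biomarker plan allows a high/low Fisher test with no stated cut-point or role, while the stated 80% power belongs only to the t-test on continuous change

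*Combined protocol and SAP*

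**What the plan says.** Section 2.3 (Secondary Efficacy Endpoints, item 6) defines the endpoint as a change: "We will examine the effect of pravastatin on change in serum biomarkers including cytokines, chemokines, soluble receptors, and proteins", followed by ten named markers. It defines no high or low category.

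Section 9.3.2 (Change in biomarkers) sets out the analysis:

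- The main test, with visits counted in months: "Two-sample t-test will be carried out to compare the change in biomarkers from baseline to each of the two follow-up time points, 6 and 12". The Mann-Whitney test takes over when distributions are highly skewed.
- The binary test: "Fisher exact test will be used for dichotomous stratifications (high versus low").
- The power claim: "data from 47 patients per group achieve 80% power to detect an effect size of 0.72". The test and level behind that claim, corrected for the number of markers only, are given as: "two-sided two-sample t-test with a Bonferroni corrected 0.01 level of significance since we plan to test 10 biomarkers (0.1 / 10"). The effect size is defined for a continuous change: "the effect size is the ratio between the difference in change of biomarkers between the two groups over SD(diff").
- The adjusted analysis: "Linear or logistic regression analysis will be carried out if there is evidence of imbalance between the two groups". A logistic model implies a binary outcome here too.

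The 47 per group is the general analytic sample of section 9.2: "Analytic sample = 94 (47:47) after 28% drop-out".

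**The concern.** The endpoint and its power calculation are continuous, but the plan also permits a test on a two-category version of the same markers and leaves that version open. It does not name the markers to be split, the variable that is cut (level or change), the visit, the cut-point or the significance level. It also does not say whether Fisher's test stands in for the t-test or beside it.

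Two different things are at stake, depending on that last choice:

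- If Fisher's test **replaces** the t-test for a marker, the 80% does not apply to that marker, because splitting a continuous change discards information.
- If Fisher's test **supplements** the t-test, the marker has an additional route to significance that the divisor of 10 does not count. The size of this problem depends on whether the cut is fixed before the data are seen.

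**Working it through.** **Inputs from the protocol.** n = 47 per group, effect size d = 0.72 in units of the SD of change, two-sided α = 0.01 = 0.1/10, ten markers, two follow-up visits (section 9.3.2).

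**Assumptions, not in the protocol.** Change scores are Normal with equal SD in both groups, and the change is what is cut. The cut-point is unknown, so it is varied.

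**1. Reproduce the stated power.** Noncentral t with df = 2 × 47 − 2 = 92 and noncentrality 0.72 × √(47/2) = 3.49; the critical value is 2.63. Power = 80.3%. The stated 80% holds.

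**2. Power of Fisher's test at the same shift.** For a cut c, measured from the mean of the lower group in SD units, the proportions above it are 1 − Φ(c) and 1 − Φ(c − 0.72). Power is the summed probability of all 48 × 48 possible tables with two-sided Fisher p ≤ 0.01.

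| Cut on the change | Proportions high | Fisher power |
|---|---|---|
| Pooled median (c = 0.36) | 35.9% vs 64.1% | 48.1% |
| Control median | 50% vs 76.4% | 46.5% |
| Pooled tertile | 20.6% vs 46.0% | 44.7% |
| Control 85th percentile | 15.0% vs 37.6% | 38.3% |
| Pooled quartile | 14.0% vs 36.0% | 37.1% |
| Pooled 20th/80th percentile | 10.4% vs 29.6% | 31.5% |
| Pooled 10th/90th percentile | 4.2% vs 15.8% | 13.3% |

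The median cut is the best of these. The Mann-Whitney test, simulated under the same conditions, has about 78%.

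**3. Sensitivity to the assumptions.** The table treats the cut as a fixed value. Placing it at the observed pooled median or quartiles gives about 44-46% by simulation, still under the 48% ceiling. If the follow-up level is cut instead of the change, the shift becomes 0.72 × √(2(1 − ρ)), where ρ is the baseline-to-follow-up correlation (equal variances assumed). The protocol gives no ρ. With a midpoint cut, Fisher power is 86% at ρ = 0, 67% at 0.3, 48% at 0.5, 25% at 0.7 and 6% at 0.9. The 48% ceiling therefore belongs to a cut on the change.

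**4. Sample size needed at the median cut.** n = [2.576 × √(2 × 0.5 × 0.5) + 0.842 × √(0.359 × 0.641 + 0.641 × 0.359)]² / 0.281² ≈ 73 per group (80 with continuity correction), against 47.

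**5. False positives if the split supplements the t-test** (simulated with no true effect, one marker, one visit, each test at 0.01):

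- t-test alone: about 0.010
- t-test or one median split: about 0.012
- t-test or the best of three quartile cuts: about 0.023
- t-test or the best of five cuts: about 0.028

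**6. The divisor.** Ten tests at 0.01 give a Bonferroni bound of 0.10. Ten markers at two visits make 20 tests: bound 20 × 0.01 = 0.20, or 1 − 0.99²⁰ = 0.18 if independent. This arises from the t-tests alone.

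**The case against.** The strongest reply is that section 9.3.2 only matches the test to the form of the data: t-test for continuous, Mann-Whitney for skewed, Fisher's test for anything binary. On that reading nobody has committed to splitting all ten markers, and the logistic model is likewise conditional on imbalance. That is fair. A reader might infer that every marker is to be cut as well as tested continuously; the text does not say so.

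A reader might also infer that the split both cuts the planned power and adds tests. Those harms belong to different readings: power is lost where Fisher's test replaces the t-test, and tests are added where it supplements it. Where the t-test is run, it keeps 80%.

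A third tempting inference is a large family-wise inflation. Over ten independent markers at one visit, a best-of-five search would give about 1 − (1 − 0.028)¹⁰ = 0.25. But no section plans a search for cuts, the independence of the markers is assumed, and a single median split gives only 1 − (1 − 0.012)¹⁰ = 0.11.

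Finally, these are secondary endpoints in a phase II screening design, and the Laboratory Manual, which is not part of the documents, might contain thresholds. This limits the weight of the point. It does not supply the missing specification, and a choice by form of data still does not explain why a marker whose endpoint is continuous change would become binary.

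**Conclusion.** The point holds in limited form. The plan permits a less powerful test on an undefined split of an endpoint that it defines and powers as continuous change.

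A biomarker conclusion that rests on a split of the change would have at most about 48% power at the plan's own effect size, about 37-38% at quartile-type cuts fixed in advance, and as little as 13% at the pooled 10th or 90th percentile. These figures assume Normal change scores with equal SD; they are not derivable from the protocol alone. They describe Fisher's test only.

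The effect on false positives is negligible for one median cut and roughly a two- to threefold rise per marker if the cut is the best of three to five. The second case is left open by the text, not planned by it.

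The larger and more certain multiplicity gap is the uncounted second visit. It exists without any Fisher test, so the high/low analysis should not be blamed for the whole departure from 0.10.

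**What to change.** In section 9.3.2 (Change in biomarkers), state that each biomarker conclusion rests on the continuous analysis of change, or on the rank test already named if the distribution is highly skewed. Present any high/low tables descriptively, without p-values, and drop the logistic model for these markers. Keep a binary test only for a marker that is mostly below its detection limit, with that limit as the cut.

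In the same paragraph, settle the two visits, since removing Fisher's test leaves them uncounted. Either name one visit for the corrected tests or divide by 20. Dividing by 20 (level 0.005) takes the t-test power at an effect size of 0.72 from 80.3% to 72.9%.

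The high/low change costs wording only, with no new data or patients. The downside is that high/low results are no longer reported with p-values.
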